15.2 SCHEDULE OF LABORATORY TESTS

	Schedule of Laboratory Tests								
	Screening	Run-In		Treatment Period					End-of-Treatment
				V2 [Period 1] / V3 [Period 2] / V4 [Period 3]					
Study Day(s) (± 1 day)	V1	V1.5	V1.2, V1.6	D1, D29, D57	D3, D10, D17, D26, D31, D38, D45, D54, D59, D66, D73, D78	D15, D43, D71	D24, D52, D80	D82	D96 \pm 3
Proteomics and b2M									
	Blood sample for b2M (local lab for screening only)	X							
	Blood sample for plasma proteomics (research sample)		X					X	X
	b2M (research sample)		X					X	X
Serum Pregnancy		X	X (V1.5 or V1.6)						X
Hematology									
	Complete blood count (CBC)	X			X				X
	Neutrophils	X			X				X
	Total lymphocytes	X			X				X
	Monocytes	X			X				X
	Eosinophils	X			X				X
	Basophils	X			X				X
	Iron	X			X				X
	Hemoglobin (HgB)	X			X		X		X

		Schedule of Laboratory Tests									
		Screening	Run-In		Treatment Period					End-of-Treatment	End-of-Study
					V2 [Period 1] / V3 [Period 2] / V4 [Period 3]						
Study Day(s) (± 1 day)		V1	V1.5	V1.2, V1.6	D1, D29, D57	D3, D10, D17, D26, D31, D38, D45, D54, D59, D66, D73, D78	D15, D43, D71	D24, D52, D80	D82	D96±3	
Chemistry											
	Sodium	X			X					X	
	Calcium (Total)	X			X					X	
	Potassium	X			X					X	
	Chloride	X			X					X	
	Bicarbonate	X			X					X	
	Blood urea nitrogen (BUN)	X		X	X	X			X	X	
	Creatinine	X		X	X	X			X	X	
	Protein (total)	X			X					X	
	Albumin	X			X					X	
	Bilirubin (total)	X			X					X	
	Aspartate transaminase (AST)	X			X					X	
	Alanine aminotransferase (ALT)	X			X					X	
	Gamma-glutamyl transpeptidase (GGT)	X								X	
	Alkaline phosphatase (ALP)	X								X	
	Amylase	X								X	
	Lipase	X								X	
	Lactate dehydrogenase (LDH)	X								X	
	Creatine kinase (CK)	X								X	
	Glucose	X			X					X	
	Hemoglobin A1c (HbA1c)	X								X	
	Phosphate	X			X					X	

		Schedule of Laboratory Tests									
		Screening	Run-In		Treatment Period					End-of-Treatment	End-of-Study
					V2 [Period 1] / V3 [Period 2] / V4 [Period 3]						
Study Day(s) (± 1 day)		V1	V1.5	V1.2, V1.6	D1, D29, D57	D3, D10, D17, D26, D31, D38, D45, D54, D59, D66, D73, D78	D15, D43, D71	D24, D52, D80	D82	D96±3	
	Magnesium	X								X	
	Cholesterol	X								X	
	Triglycerides	X								X	
	High-density lipoprotein (HDL)	X								X	
	Low-density lipoprotein (LDL)	X								X	
Coagulation											
	Prothrombin time/international normalized ratio (PT/INR)	X			X					X	
	Activated partial thromboplastin time (aPTT)	X			X	X			X	X	
Serology											
	Hepatitis B surface/core antigen (HBsAg)	X									
	Hepatitis C antibody (HCV Ab)	X									
	Human immunodeficiency virus antibody (HIV Ab, HIV1/HIV-2)	X									
Other Clinical Labs											
	Thyroid-stimulating hormone (TSH ultrasensitive)	X								X	

17 APPENDICES

APPENDIX 17.1 ESCALATION, DE-ESCALATION, AND DISCONTINUATION RULES FOR TREATMENT WITH AKST1210 OR CONTROL

The following definitions are relevant to evaluating whether to escalate, de-escalate, or discontinue a subject:

- **Intradialytic hypotension/hypotensive event (IDH):** A decrease in SBP \geq 20 mm Hg or a decrease in MAP \geq 10 mm Hg associated with symptoms that include: abdominal discomfort; yawning; sighing; nausea; vomiting; muscle cramps; restlessness; dizziness or fainting; and anxiety ([K/DOQI Workgroup 2005](#)).
- **Expected IDH Rate:** The expected number of occurrences of IDH per 4-week treatment period used to assess escalation, de-escalation, and discontinuation. Expected IDH is derived from a subject's Historical IDH Rate (see table below).
- **Historical IDH Rate:** The number of occurrences of IDH as documented in a subject's medical record during a recent, consecutive 8-week interval prior to randomization. This 8-week period may include the 2-week Run-in. Subjects with 5 or more IDH events during this 8-week interval will be excluded.

The table below provides the corresponding Expected IDH Rate based on the Historical IDH Rate and summarizes the rules for escalation, de-escalation, or discontinuation based on the number of occurrences of IDH.

Historical IDH Rate over 8 weeks	Expected IDH Rate over 4 weeks	Escalation Rule	De-escalation or Discontinuation Rule
0	0	1 or less	2 in 4 weeks
1	1	2 or less	3 in 4 weeks
2	1		
3	2	3 or less	4 in 4 weeks
4	2		

Escalation Rules: A subject may be escalated to the next larger column size if they experience no more than 1 IDH event above their Expected IDH Rate in a 4-week treatment period and has an Hgb level \geq 9 g/dL.

De-escalation Rules: A subject should be de-escalated to a previously tolerated column size if at any time during a 4-week treatment period they experience 2 or more IDH events above the Expected IDH Rate and/or has a Hgb level $<$ 9 g/dL despite optimized ESA treatment.

Discontinuation Rules: A subject should be discontinued if they experience 2 or more IDH events above their Expected IDH Rate in a 4-week treatment period after de-escalation to the lowest column size (AKST1210 S-15) and/or has an Hgb level $<$ 9 g/dL despite optimized ESA treatment after de-escalation to the lowest column size (AKST1210 S-15). Subjects may also be discontinued at any time at the discretion of the investigator.

As a reminder, all occurrences of IDH after the time of consent should be recorded as AEs. Refer to [Section 8](#) for additional information concerning safety reporting.

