7.1.1.1.5 Screening and Run-In Laboratory Evaluations

Biological samples will be collected and analyzed at Screening and Run-In. Blood will be drawn by a qualified medical provider. Labs will be completed by the site's local laboratory. Samples for Screening labs should be collected either on a non-dialysis day or prior to HD. For additional information, refer to [Section 15.2 Schedule of Laboratory Tests](#).

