AKST1210 S-15 or control	X	X	X	X	X	X	X	X	X	X	X	X
Vitals signs ³	X	X	X	X	X	X	X	X	X	X	X	X
Targeted physical exam	X	X	X	X	X	X	X	X	X	X	X	X
Weight	X	X	X	X	X	X	X	X	X	X	X	X
Laboratory tests (local lab) ⁴	X	X			X		X	X				X
Cogstate test battery, FACIT, PSQI, SF-36	X											
Blood samples for b2M ⁵												X
Blood samples for plasma proteomics ⁶												X
Assessment of fluid status ⁷	X	X	X	X	X	X	X	X	X	X	X	X
Adverse events and concomitant medications	X	X	X	X	X	X	X	X	X	X	X	X
Monitor tolerability per Appendix 17.1	X	X	X	X	X	X	X	X	X	X	X	X ⁸

1. Assess tolerability of Run-in period prior to randomization (see [Section 5.2](#)).
2. Refer to the Device Procedures Manual for guidance.
3. Vital signs to be collected at multiple timepoints, see [Section 7.1.1.2.2](#).
4. For additional information, see [Section 7.1.1.2.5](#) and [Section 15.2 Schedule of Laboratory Tests](#).
5. For additional information, see [Section 7.1.1.1.9](#) and [Section 15.2 Schedule of Laboratory Tests](#).
6. For additional information, see [Section 7.2.2.1](#) and [Section 15.2 Schedule of Laboratory Tests](#).
7. For additional information, see [Section 7.1.1.2.3](#).
8. Post HD, if subject has not already been discontinued, evaluate for escalation to S-25 per [Appendix 17.1](#).

SECTION 15.1.3 TREATMENT PERIOD 2 (VISIT 3/MONTH 2)

Procedures												
Visit	Visit 3: Treatment Period 2											
Visit Number	3.1	3.2	3.3	3.4	3.5	3.6	3.7	3.8	3.9	3.10	3.11	3.12
Study Week	Week 5			Week 6			Week 7			Week 8		
Study Day (± 1 day)	29	31	33	36	38	40	43	45	47	50	52	54
HD (250 mL/min for ~ 4 h)	X	X	X	X	X	X	X	X	X	X	X	X
AKST1210 S-25 or control	X	X	X	X	X	X	X	X	X	X	X	X
Vitals signs ¹	X	X	X	X	X	X	X	X	X	X	X	X
Targeted physical exam	X	X	X	X	X	X	X	X	X	X	X	X
Weight	X	X	X	X	X	X	X	X	X	X	X	X
Laboratory tests (local lab) ²	X	X			X		X	X				X
Cogstate test battery, FACIT, PSQI, SF-36	X											
Blood samples for b2M ³												X
Blood samples for plasma proteomics ⁴												X
Assessment of fluid status ⁵	X	X	X	X	X	X	X	X	X	X	X	X
Adverse events and concomitant medications	X	X	X	X	X	X	X	X	X	X	X	X
Monitor for de-escalation or discontinuation per Appendix 17.1	X	X	X	X	X	X	X	X	X	X	X	X ⁶

1. Vital signs to be collected at multiple timepoints, see [Section 7.1.1.2.2](#).

2. For additional information, see [Section 7.1.1.2.5](#) and [Section 15.2 Schedule of Laboratory Tests](#).

3. For additional information, see [Section 7.1.1.1.9](#) and [Section 15.2 Schedule of Laboratory Tests](#).

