4. For additional information, see [Section 7.2.2.1](#) and [Section 15.2 Schedule of Laboratory Tests](#).

5. For additional information, see [Section 7.1.1.2.3](#).

6. Post HD, if subject has not already been de-escalated or discontinued, evaluate for escalation to S-35 per [Appendix 17.1](#).

SECTION 15.1.4 TREATMENT PERIOD 3 (VISIT 4/MONTH 3)

Procedures												End of Tx
Visit	Visit 4: Treatment Period 3											End of Tx
Visit Number	4.1	4.2	4.3	4.4	4.5	4.6	4.7	4.8	4.9	4.10	4.11	4.12
Study Week	Week 9			Week 10			Week 11			Week 12		
Study Day (± 1 day)	57	59	61	64	66	68	71	73	75	78	80	82
HD (250 mL/min for ~ 4 h)	X	X	X	X	X	X	X	X	X	X	X	
AKST1210 S-35 or control	X	X	X	X	X	X	X	X	X	X	X	
Vitals signs ¹	X	X	X	X	X	X	X	X	X	X	X	
Targeted physical exam	X	X	X	X	X	X	X	X	X	X	X	
Weight	X	X	X	X	X	X	X	X	X	X	X	
Laboratory tests ²	X	X			X		X	X		X		
Cogstate test battery, FACIT, PSQI, SF-36	X											
Blood samples for b2M ³												X
Blood samples for plasma proteomics ⁴												X
Assessment of fluid status ⁵	X	X	X	X	X	X	X	X	X	X	X	
Adverse events and concomitant medications	X	X	X	X	X	X	X	X	X	X	X	
Monitor for de-escalation or discontinuation per Appendix 17.1	X	X	X	X	X	X	X	X	X	X	X	

Refer to
Section
15.1.5

1. Vital signs to be collected at multiple timepoints, see [Section 7.1.1.2.2](#).

2. For additional information, see [Section 7.1.1.2.5](#) and [Section 15.2 Schedule of Laboratory Tests](#).

3. For additional information, see [Section 7.1.1.1.9](#) and [Section 15.2 Schedule of Laboratory Tests](#).

4. For additional information, see [Section 7.2.2.1](#) and [Section 15.2 Schedule of Laboratory Tests](#).

5. For additional information, see [Section 7.1.1.2.3](#).

SECTION 15.1.5 END OF TREATMENT AND END OF STUDY VISITS

Procedures	Visit	Visit 5: End of Treatment	Visit 6: End of Study (EOS)
Study Week		Week 12 (continued)	Week 14
Study Day		Day 82 ± 1	Day 96 ± 3
Targeted physical examination		X	X
Weight		X	X
12-lead ECG			X
Vital signs ¹		X	X
Laboratory tests ²		X ²	X ³
Serum pregnancy test (WOCBP only)			X
HD		250 mL/min flow rate for ~4h	X (flow rate per standard of care)
AKST1210 or Control		X	
MoCA, PHQ-9			X
Cogstate test battery, FACIT, PSQI, SF-36		X	X
Blood sample for b2M ⁴			X
Blood sample for plasma proteomics ⁵			X
Assessment of fluid status ⁶		X	X
Adverse events and concomitant medications		X	X

1. For additional information, see [Section 7.1.1.2.2](#).

2. Refer to [Section 15.2 Schedule of Laboratory Tests](#).

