4.7 Study Assessment Time Points

The study consists of 6 protocol-specified visits which will be assessed as nominal visits from an analysis perspective:

- 1) Visit 1 Screening/Run-In: screening will be conducted at Days -42 to -14 and run-in will be conducted at Days -14 to -1.
- 2) Visit 2 Treatment Period 1 (Weeks 1- 4): randomization occurs on the same day as Day 1 and the first use of the device/control. Tolerability is monitored during each hemodialysis session. Evaluation for escalation, or discontinuation will be performed on Day 26.
- 3) Visit 3 Treatment Period 2 (Weeks 5- 8): Evaluation for de-escalation, escalation, or discontinuation will be performed on Day 54. Monitoring for de-escalation or discontinuation is assessed during each hemodialysis session.
- 4) Visit 4 Treatment Period 3 (Weeks 9- 12). Monitoring for de-escalation or discontinuation is assessed during each hemodialysis session.
- 5) Visit 5 End of Treatment (EOT) (Week 12, Day 82)

- 6) Visit 6 EOS (Week 14): In the event of early termination of a subject who has received at least 1 treatment, the end of study procedures will be performed unless the subject has withdrawn consent.

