5.7.6 Incidence of Anemia Leading to De-escalation or Discontinuation

The number and percentage of subjects with any anemia leading to de-escalation or discontinuation from AKST1210/control will be summarized by treatment group and Total.

5.7.7 Change from Baseline in Levels of b2M, Evaluation of Change Based on Column Size

Blood sampling for b2M concentration will occur at Run-in, during the treatment period, and at EOS. During the treatment period, blood samples will be collected at 3 sample locations (A, B, C, [Figure 2](#)) and at multiple time points prior to dialysis (PTD), at 1 hour, 2 hours, and at the end of dialysis (EOD) at the end of each 4-week treatment (V2.11, V3.11 and V4.11). Detailed collection schedule could be found in [Figure 2](#) and [Table 1](#).

[figure not shown]

Figure 2. The b2M sample locations in the control and the AKST1210 group.

Table 1. Collection schedule of b2M samples

| Study period | Run-in | Treatment period | | | | | | | | | | End of study | |
|-----------------|--------|----------------------|--------|---------|-----|----------------------|--------|---------|-----|----------------------|--------|--------------|---------------|
| Study visit | V1.5 | V2.11 | | | | V3.11 | | | | V4.11 | | | V6 |
| Study week(day) | | Week 4 (D4) | | | | Week 8 (D52) | | | | Week 12 (D80) | | | Week 14 (D96) |
| Column size | | 150 mL column (S-15) | | | | 250 mL column (S-25) | | | | 350 mL column (S-35) | | | |
| Timepoint | PTD | PTD | 1 hour | 2 hours | EOD | PTD | 1 hour | 2 hours | EOD | PTD | 1 hour | 2 hours | PTD |
| Sample location | A | A | A,B,C | A,B,C | A | A | A,B,C | A,B,C | A | A | A,B,C | A,B,C | A |

PTD: prior to dialysis; EOD: end of dialysis. Sample location A is before the AKST1210 column. Sample location B is after the AKST1210 column and before the hemodialyzer. Sample location C is after both the AKST1210 column and the hemodialyzer. In the control group, because there is no AKST1210 column, sample location A is the same as sample location B ([Figure 2](#)).

Three hypotheses will be tested to evaluate the effects of AKST1210 columns on b2M removal, including overall removal after AKST1210 treatment and instantaneous removal during AKST1210 treatment.

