5.8.6 Laboratory Data

Analyses on hematology, chemistry, coagulation, and other clinical lab tests will consist of the following (included in DSMB):

- Observed values at baseline and each scheduled post-baseline time point, along with change from baseline at each scheduled post-baseline time point

- Number and percentage of subjects with abnormal laboratory tests indicating serious condition at each scheduled time point
- Shift tables, by analyte and by out-of-range flag at each scheduled post-baseline time point compared to baseline per subject, may be produced

Hematology: complete blood count (CBC), neutrophils, total lymphocytes, monocytes, eosinophils, basophils, iron, hemoglobin (Hgb) will be collected at Visit 1, Visit 2 Treatment Period 1, Visit 3 Treatment Period 2, Visit 4 Treatment Period 3, Visit 5 End of Treatment, and Visit 6 EOS.

Chemistry: sodium, calcium (Total), potassium, chloride, bicarbonate, protein (total), albumin, bilirubin (total), aspartate transaminase (AST), alanine aminotransferase (ALT), glucose, and phosphate will be collected at Visit 1, Visit 2 Treatment Period 1, Visit 3 Treatment Period 2, Visit 4 Treatment Period 3, and Visit 6 EOS. Blood urea nitrogen (BUN), creatinine will be collected at Visit 1, Visit 2 Treatment Period 1 Day 1/3/10/17/26, Visit 3 Treatment Period 2 Day 29/31/38/45/54, Visit 4 Treatment Period 3 Day 57/59/66/73/78, Visit 5 End of Treatment, and Visit 6 EOS. Gamma-glutamyl transpeptidase (GGT), alkaline phosphatase (ALP), amylase, lipase, lactate dehydrogenase (LDH), creatinine kinase (CK), hemoglobin A1c (HbA1c), magnesium, cholesterol, triglycerides, high-density lipoprotein (HDL), low-density lipoprotein (LDL), and will be collected at Visit 1 and Visit 6 EOS.

Coagulation: Prothrombin time/ international normalized ratio (PT/INR) will be collected at Visit 1, Visit 2 Treatment Period 1, Visit 3 Treatment Period 2, Visit 4 Treatment Period 3, and Visit 6 EOS. Activated partial thromboplastin time (aPTT) will be collected at Visit 1, Visit 2 Treatment Period 1 Day 1/3/10/17/26, Visit 3 Treatment Period 2 Day 29/31/38/45/54, Visit 4 Treatment Period 3 Day 57/59/66/73/78, and Visit 6 EOS.

Other: Thyroid-stimulating hormone (TSH ultrasensitive) will be collected at Visit 1 and Visit 6 EOS.

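### Escalation on Day 26 and Day 54 requires Hgb of at least 9 g/dL, but the latest scheduled Hgb is then 11 days old, and no visible text requires the next result before the larger column is connected

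*Protocol*

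**What the plan says.** Appendix 17.1 sets two conditions for escalation: the subject has had "no more than 1 IDH event above their Expected IDH Rate in a 4-week treatment period and has an Hgb level" of at least 9 g/dL. It gives no sampling day and no maximum age for the Hgb value.

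The decision time is fixed elsewhere:
- Protocol 15.1.2, footnote to V2.12 (Day 26): "Post HD, if subject has not already been discontinued, evaluate for escalation to S-25".
- Protocol 15.1.3, footnote to V3.12 (Day 54): "Post HD, if subject has not already been de-escalated or discontinued, evaluate for escalation to S-35".
- SAP 4.7 agrees: "Evaluation for escalation, or discontinuation will be performed on Day 26", with Day 54 given for Period 2.

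In Protocol 15.2 the Hgb row is marked, within the treatment periods, on D1/D29/D57 and D15/D43/D71. The draw on Days 26 and 54 is for other tests. SAP 5.8.6 states that "Blood urea nitrogen (BUN), creatinine will be collected at Visit 1, Visit 2 Treatment Period 1 Day 1/3/10/17/26", and aPTT follows the same days within Period 1. Hgb and CBC are not in that column.

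On timing relative to dialysis, Protocol 7.1.1.1.5 says "Samples for Screening labs should be collected either on a non-dialysis day or prior to HD", and a 15.1.1 footnote sets pre-dialysis timing for the run-in BUN, creatinine and aPTT samples. Nothing comparable is stated for treatment-period Hgb.

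The later safeguard is the de-escalation rule in Appendix 17.1. A subject "should be de-escalated to a previously tolerated column size if at any time during a 4-week treatment period" the IDH threshold is crossed, or Hgb is below 9 g/dL despite optimized ESA treatment.

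**The concern.** The protocol sets a safety limit on a laboratory value, but its visible schedule supplies no current value when the limit is applied. A subject in the active arm whose Hgb falls below 9 g/dL in the second half of a period can pass the check on an older result. Extracorporeal volume then rises from 65 to 105 mL (S-25) or from 105 to 177 mL (S-35), per Protocol Table 2. Controls have no column in the circuit, so the exposure concerns the active arm only.

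The revision history shows that this limit was intended. Version 2.0 added the bar on escalating subjects below 9 g/dL, and added Hgb tests to help watch for anemia. The added mid-period tests do not line up with the decision days.

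There is a smaller consequence for analysis. SAP 5.7.5 summarizes worsening anemia by column size. A fall late in one period but first measured on Day 29 or Day 57 could be counted against the larger column.

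**Working it through.** The documents state no age for the Hgb value, so there is no figure to reproduce. The check is day arithmetic on the schedule.

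**Reading of the schedule.** In the text available, the Hgb row of 15.2 is one cell short of the header, but the uncertainty is confined to the end-of-treatment and end-of-study cells. The treatment-period marks are corroborated: the V2.1 revision entry gives local testing on Days 15, 43 and 71, and the BUN row, which is complete, matches the days in SAP 5.8.6.

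**Inputs.** Decisions on Days 26 and 54. First use of the larger column on Days 29 and 57. Scheduled Hgb on Days 1, 15, 29, 43, 57 and 71. Each visit has a window of ±1 day.

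**Age at the decision** = decision day − last scheduled Hgb day.
- Period 1: 26 − 15 = 11 days. Period 2: 54 − 43 = 11 days.
- With windows: 25 − 16 = 9 to 27 − 14 = 13 days.

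**Age at first use of the larger column**, if the same-day value is not awaited: 29 − 15 = 57 − 43 = 14 days (12 to 16 with windows).

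**Sessions reflected.** A Day 15 value drawn before dialysis follows the sessions on Days 1, 3, 5, 8, 10 and 12, which is 6 of 12. Day 43 likewise follows 6 of 12.

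**With an end-of-period Hgb drawn before dialysis:**

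| | D24/D52 | D26/D54 |
|---|---|---|
| Age at decision | 26 − 24 = 2 days (1 to 4; two sessions cannot share a day) | same day |
| Sessions reflected | 10 of 12 | 11 of 12 |
| Lead time to V3.1/V4.1 | 29 − 24 = 5 days (3 to 7) | 29 − 26 = 3 days (28 − 27 = 1 to 30 − 25 = 5) |

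The Period 2 intervals are the same.

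**Volume step.** 105 − 65 = 40 mL (40/65 = 62%). 177 − 105 = 72 mL (72/105 = 69%).

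**Ceiling on decisions affected.** Two per active subject: 26/2 × 2 = 26 if everyone enrolled is randomized and reaches both decisions, or 10 × 2 = 20 on the evaluable number. This counts decisions, not expected breaches.

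**The case against.** The strongest objection is that the gap may be closed in text we cannot see. The revision history says Section 2.3.1 Table 1 was made more explicit on anemia mitigation, and Protocol 7.1.1.1.6 sends sites to that table. The Device Procedures Manual is not supplied either. A reader might infer that the trial has no anemia check before a column change. The documents do not support that; they show only that the visible schedule contains none.

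A reader might also infer that the plan tells investigators to escalate on the Day 15 or Day 43 value. It does not. Appendix 17.1 is permissive and names no value, and unscheduled Hgb is not barred. What stands is that no later value is scheduled.

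The Day 29 or Day 57 sample could serve as a gate if drawn and resulted before connection. URR in SAP 5.8.1 needs a pre-dialysis BUN and those draws include BUN, which hints at pre-dialysis sampling. It is a hint, not a requirement, and says nothing about when the result returns.

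Backstops reduce the harm. De-escalation can be triggered at any time in a period, clinically significant values must be followed (Protocol 7.2.1), pre- and post-dialysis hematocrit is among the SAP 5.8.1 parameters, and the investigator may discontinue a subject. If a Day 29 value is below 9 g/dL, ESA is already optimized and the result returns in 1 to 3 days (assumed), the subject has 1 to 2 sessions on the larger column (Day 29, or Days 29 and 31).

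A longer exposure is tempting to claim: 6 sessions (Days 29, 31, 33, 36, 38 and 40) before the Day 43 draw. That needs ESA not yet optimized and no retest for two weeks, and it arises mainly from the ESA condition in the de-escalation rule, so it should not be charged to the sampling schedule.

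**Conclusion.** The point holds for the visible schedule. At both escalation decisions the latest protocol-scheduled Hgb is 11 days old (9 to 13 with windows), and no visible text requires the Day 29 or Day 57 result before the larger column is connected. This is more than missing detail, because the schedule as written does not support the protocol's own limit.

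Its clinical size is unknown. The documents give no rate of Hgb decline and no anemia incidence, so the number of subjects escalated below 9 g/dL cannot be estimated. The existing safeguards lessen the consequence but do not visibly close the gap at the decision. The conclusion rests on Table 1 and the Device Procedures Manual not already requiring a fresher value. The change is worth making because it is cheap and concerns a safety rule in a trial whose primary objective is safety and tolerability.

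**What to change.** Schedule an end-of-period local-lab Hgb in both arms, so that evaluations stay identical and the blind is kept. Name it in Appendix 17.1 and in the V2.12 and V3.12 footnotes as the value used for escalation. Either of two forms would do:

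- **Days 24 and 52, before dialysis.** The result should be in hand at the decision. Update the local-lab rows of 15.1.2 and 15.1.3, which are blank at V2.11 and V3.11, as well as 15.2. The tube is a separate local send, because research samples go to a biorepository (Protocol 7.1.1.1.9). Do not tie it to the b2M draw: 15.2 and SAP 5.7.7 place that at V2.11 and V3.11 ("prior to dialysis (PTD), at 1 hour, 2 hours, and at the end of dialysis (EOD) at the end of each 4-week treatment"), while 15.1.2 and 15.1.3 appear to place it one visit later.
- **Days 26 and 54, added to the local draw already taken.** Require a result of at least 9 g/dL before the larger column is connected at V3.1 or V4.1, and keep the current size until it is available. The 15.1 local-lab rows are already marked at these visits. In 15.2 these days share a column with ten others, so restrict the Hgb mark to Days 26 and 54.

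Gating on the Day 29 or Day 57 sample would need no extra tests, but it requires a result before that same session starts, and the documents give no local turnaround time.

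Cost: at most 26 × 2 = 52 Hgb tests, with no new visit and no change of threshold. If Table 1 already requires this check, carry it into 15.1 and 15.2.
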